### 8.6.4. Missing or Incomplete Survey Data

No data imputations will be performed for missing or incomplete survey data.

## 9. Study Population Summaries

All continuous variables will be summarized using the following descriptive statistics: n (non-missing sample size), mean, standard deviation, median, maximum, and minimum. The frequency and percentages (based on the non-missing sample size) of observed levels will be reported for all categorical measures.

### 9.1. Subject Disposition

Tables will present the number and percentage of subjects who fall into each of the following categories. Tables will include all subjects and the sensory and subsensory treatment arm where applicable.

- Total enrolled (all subjects)
- Total implanted (safety population-all subjects)
- Total enrolled subjects who undergo a procedure for implantation of eCoin and are randomized to a treatment arm and have data at baseline and the primary endpoint. (ITT population-all subjects, sensory arm, subsensory arm)
- Total subjects that undergo a procedure for implantation of eCoin and are randomized to a treatment arm, experience no major protocol violations or deviations from assigned therapy (Per protocol population-all subjects, sensory arm, subsensory arm)
- Early termination from the study (all subjects)
- Completed study (all subjects)

For subjects who withdraw from the study early, the number and percentage withdrawing by reason will be presented. A by-subject listing of early terminations will be presented including the last study visit completed and reason for early termination. A subject disposition flow and study schedule time points will summarize all enrolled subjects who reached various stages of the trial and their analysis population.

## 9.2. Subject Eligibility

Inclusion and exclusion criteria not met at screening (screen failures) will be presented for all screened but not enrolled subjects. Eligibility not met for enrolled subjects will also be presented. Eligibility data will be summarized in a table with the number (n) and percentage of subjects that did not meet each criterion. Subjects can be counted under multiple rows.

## 9.3. Randomization

Randomization details will be listed for all subjects in the ITT population. This listing will include the date of randomization, randomization number, block, and assigned treatment arm.

## 9.4. Premature Unblinding

The ESSENCE protocol requires patient and investigator blinding through 3 months post-activation. A by subject listing of all premature unblinding will be presented. This table will include the date of the unblinding, who was unblinded (patient vs Investigator), and the circumstances surrounding the event.

## 9.5. Protocol Deviations

Protocol deviations, which are collected throughout the study, will be summarized. A major protocol deviation is one that affects the safety of the subject or the scientific validity of the results. A minor deviation does not affect the safety of the subject or the scientific validity of the results. The frequency and percentage of patients with at least one major Protocol Deviation and minor Protocol deviation will be listed by classification and reason/category for the PD.

## 9.6. Treatment Compliance

The ESSENCE study will explore the effect of sensory and subsensory treatment arms. Significant departures from the assigned amplitude programming protocol include:

- no sensory level identified for the sensory arm
- sensory level identified at the lowest amplitude setting (0.5 mA) for the subsensory arm
- reprogramming visit prior to 3 months that is a significant departure from the assigned treatment stimulation
- device not activated
- device turned off
- A protocol deviation related to device programming does not match assigned treatment arm

Any non-compliances to the assigned treatment arm at randomization will be listed by subject. This listing will include the date of randomization, assigned treatment arm, and reason for departure, and date of treatment noncompliance.

## 9.7. Demographics and Baseline Characteristics

Demographic and baseline characteristics will be summarized by age, gender, ethnicity, race, current smoking status. Demographic and baseline characteristics will be summarized for all implanted subjects. Percentages will be calculated relative to the number of subjects in the population being presented.

OAB history will be presented. History will include duration of OAB and success of prior treatments (PTNS therapy, TENS therapy, OAB medications, and Botox). It will include duration of OAB and success of prior treatments (PTNS therapy, TENS therapy, OAB medications, anti-stress incontinence surgery, and Botox). Success will be categorized as “yes”, “no”.

Additionally, a by-question listing of multiple-choice questions on the CRF pertaining to the subject's experience with OAB will be summarized for all implanted subjects.

## 9.8. Treatment Exposure

The duration of device implantation and device activation, in weeks, will be summarized for all implanted subjects.

## 10. Efficacy Analysis

### 10.1. Primary Efficacy Analysis:

This randomized controlled double-blind study will evaluate the efficacy of eCoin in reducing episodes of UUI per day with two different treatment arms. The primary efficacy outcome is the reduction from baseline in the number of UUI episodes per day on a 3-day voiding diary (72 hours) after 3 months of eCoin device tibial nerve stimulation. The voiding diary CRF will report the total over the 3 days for each measure, which will then be averaged.

The primary efficacy analysis will be performed on the Per Protocol population. The change from baseline will be summarized with descriptive statistics (n, mean, median, standard deviation, 25th quartile, 75th quartile, minimum, and maximum). Additionally, the mean reduction of UUI episodes per day along with its two-sided 95% confidence interval will be summarized for all subjects, sensory arm, and subsensory arm. Boxplots and line graphs with observed values and change from baseline may also be presented. Treatment effect size may be reported using Cohen's d and/or relative risk to highlight the observed differences, if any.

No data imputations will be performed for subjects who do not have 3-month post-activation data. Missing and incomplete diary data will be handled per section 8.6.3 Missing or Incomplete Diary.

The primary endpoint is exploratory in nature. There are no pass/fail criteria to define the study success and there is no powered comparison between the two treatment arms

Because this study is exploring the efficacy of the eCoin System programmed using two different methodologies, the per protocol population will be analyzed for the primary endpoint. The per protocol population, as described in section 7. Analysis Populations, will exclude patients that have taken OAB medications, do not meet eligibility criteria, experience major protocol deviations and/or experience departures

from the assigned programming treatment. Due to the nature of the study, it is expected a subset of all implanted subjects will have data on the primary endpoint.

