Enrollment/Baseline: Subjects who meet eligibility criteria will first review and complete the Informed Consent Form. Then, demographic, medical history, and medication information is collected, a physical examination is completed, a PVR is done, vital signs are collected, and eligibility criteria are reviewed. Subjects should begin a 2 week wash-off of OAB medications, or 4 week wash-off of PTNS if applicable. Subjects will return for their baseline visit with a completed voiding diary and fill their baseline surveys. A final eligibility determination is made following review of the voiding diary.

Implant Visit: Implantation procedure is completed, vital signs are collected, subject is assessed for AEs and concomitant medications, and pre/post pictures are taken.

Healing Check: Check-in on healing, vital signs are collected, subject is assessed for AEs and concomitant medications, pictures are taken.
Activation: Randomization occurs and subject is activated according to their treatment arm. Vital signs are collected, subject is assessed for AEs and concomitant medications, and pictures are taken.

2 Month: The subject should complete a voiding diary in the 7 days preceding this visit. At the visit the subject will fill the OABq survey and patient satisfaction survey and be assessed for AEs and concomitant medications.

3 Month: The subject should complete a voiding diary in the 7 days preceding this visit. At the visit the subject will fill the OABq survey

and patient satisfaction survey and be assessed for AEs and concomitant medications. Then, the subject will be unblinded and reprogramming will be done if desired.

4 month: The subject should complete a voiding diary in the 7 days preceding this visit. At the visit the subject will fill the OABq survey and end of study survey and be assessed for AEs and concomitant medications.

Safety

Safety will be assessed by collection of adverse events related to the device and/or procedure, all serious adverse events, and device malfunctions.

1-2 Background

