Subjects will be randomized at activation. Approximately 4 weeks post implantation, subjects will return for the activation visit at which time they will be randomized and the device will be activated based upon their randomization group. The Valencia Technologies Field Clinical Engineers will implement the activation protocol, setting the amplitude of stimulation.

2-3-3-2 Selection Criteria

Participants will be screened in accordance with the following inclusion and exclusion criteria.

2-3-3-2-1 Inclusion Criteria

1. Women and men above 18 years old or older at time of consent
2. Individual with diagnosis of overactive bladder with urgency urinary incontinence.
3. Individual has at least one urgency urinary incontinence episode on each of three days as determined on a 3-day voiding diary.
4. Individual understood the nature of the procedure and study requirements and provided written informed consent.
5. Individual is willing to comply with specified protocol requirements and follow-up evaluations.
6. Individual is intolerant of or has an inadequate response to any of anticholinergics, β 3-adrenoceptor agonists, onabotulinumtoxinA, or who have undergone percutaneous tibial nerve stimulation (PTNS).
7. Individual is determined to be a suitable surgical candidate by physician.

2-3-3-2-2 Exclusion Criteria

1. Individual is not appropriate for eCoin therapy based upon the US FDA-approved IFU requirements.
2. Individual has predominantly stress urinary incontinence (greater than 1/3 of leaks on baseline diary are stress).
3. Individual has clinically significant bladder outlet obstruction.
4. Individual has an active urinary tract infection at time of enrollment or has had four or more symptomatic UTI's in the last 12 months.
5. Individual has microscopic hematuria that has not been evaluated.
6. Individual has significant lower urinary tract pain or has been diagnosed with interstitial cystitis or bladder pain syndrome that is actively being managed.
7. Individual has post void residual greater than 200 cc.
8. Individual has an active diagnosis of bladder, urethral, or prostate cancer.
9. Individual has had a prior anti-stress incontinence surgery within the last year.
10. Individual is pregnant, breast feeding, is less than 12 months post-partum or intends to become pregnant during the study.
11. Individual has uncontrolled diabetes mellitus (Hemoglobin A1C > 7).

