### 5.2.1. Eligibility Criteria

#### Inclusion Criteria

- Women and men above 18 years old or older at time of consent
- Individual with diagnosis of overactive bladder with urgency urinary incontinence.
- Individual has at least one urgency urinary incontinence episode on each of three days as determined on a 3-day voiding diary.
- Individual understood the nature of the procedure and study requirements and provided written informed consent.
- Individual is willing to comply with specified protocol requirements and follow-up evaluations.
- Individual is without pharmacological treatment of overactive bladder (anticholinergic and  $\beta$ 3-adrenoceptor agonists) for 2 weeks prior to baseline.
- Individual is intolerant of or has an inadequate response to any of anticholinergics,  $\beta$ 3-adrenoceptor agonists, onabotulinumtoxinA, or who have undergone percutaneous tibial nerve stimulation (PTNS).
- Individual is determined to be a suitable surgical candidate by physician.

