#### **5.4. Schedule of Assessments**

The enrollment process consists of obtaining informed consent, screening, completing baseline evaluation, implanting the eCoin system, and establishing the participant's amplitude setting. Follow up assessments will occur at 2- and 3-months post activation. The patient and investigator unblinding will occur at the end of the 3 months visit and a final follow up visit will occur at 4 months post-activation. A revision procedure would not reset the initial activation date.

For visits involving a 3-day voiding diary, the diary should be completed over 3 consecutive days during the 7 days prior to the indicated visit. The timing windows associated with each visit number is described below.

- Visit 1: Screening Procedures (informed consent, demographic and medical history and concomitant medication/therapy information, physical examination, and vital signs are collected, subjects begin 2 week wash-off of OAB medications or 4 week wash-off of PTNS if applicable, eligibility determination)
- Visit 2: Baseline Assessments (3-day voiding diary, OABq, patient satisfaction survey, concomitant therapy review, final eligibility determination) (Time: Between 3 and 32 days from Visit 1)

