We plan to use the per protocol population as our primary analysis population. This is due to the concern that the Intent to Treat (ITT) population will be diluted due to deviations from the assigned therapy. To adjust for noncompliance/nonadherence, we must estimate the proportion from the subsensory group who will have a sensory level that is cannot be reduced by 25% (i.e. their sensory threshold is the minimum setting of 0.5 mA). Based on the Pivotal trial, 3.85% (n=130) had a sensory threshold of 0.5 mA. Since this scenario only affects the subsensory arm, we estimate this this proportion to be 0.02. Additionally, in the subsensory threshold group, we must adjust for patients who have no sensory threshold, (i.e. they do not feel sensation at any amplitude level and therefore are unable to identify the sensory setting). Based on the Pivotal trial, 6.15 % (n=130) had a sensory threshold of “not identified.” Since this scenario only affects the sensory arm, we estimate this scenario to be 0.03. Lastly, we plan for a 10% dropout rate.

[figure not shown]
Considering the scenarios described above, a sample size of n=16 will have a precision of 1.07. For this analysis, we are considering a low assumed treatment effect as a mean reduction of 1.3. This is the 3rd quartile of mean reduction from the pivotal trial at 2 months, meaning 75% of the data lies below -1.3. The mean reduction from 8 weeks is being used for this analysis because in the pivotal study, patients had the option to reprogram at 8 weeks, therefore the 12 week results are confounded by reprogramming. Since the precision of 1.07 is below our assumed treatment effect of 1.3, the confidence interval (0.23, 2.37) does not include zero. This means if the treatment is effective, we expect to have sufficient sample size to see a result. Accounting for 15% of patients taken out of the Per Protocol population due to withdrawal or deviations from the assigned therapy group, a sample size of 13 per arm has a precision of 1.21 which is less than 1.3 UUI.

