### 8.1. Key Definitions

#### 8.1.1. Baseline

Baseline efficacy measures will be defined as the last measure taken up to and including the baseline visit (Visit 2). Baseline safety measures will be defined as the last measure taken prior to device implantation.

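### With a selected baseline and no unstimulated arm, each arm's mean reduction exceeds zero under no effect, yet the sample-size text treats an interval excluding zero as seeing an effect

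*SAP*

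**What the plan says.** **Selection.** Inclusion criterion 3 (protocol 2-3-3-2-1, repeated in SAP 5.2.1) requires "at least one urgency urinary incontinence episode on each of three days as determined on a 3-day voiding diary". The protocol synopsis, under Enrollment/Baseline, adds: "A final eligibility determination is made following review of the voiding diary". The visit schedules in both documents show one diary before implant, the one returned at Visit 2.

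**Baseline.** SAP 8.1.1 defines baseline efficacy as the "last measure taken up to and including the baseline visit (Visit 2"). SAP 8.2.5 measures change from that value, and SAP 10.4.1 applies its 50% rule to it.

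**Arms.** Sensory and subsensory are both active settings (SAP 5.1). Protocol 2-3-4 confirms that every subject is stimulated.

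**How the per-arm result is read.** SAP section 6, with near-identical text in protocol 2-6-5, calls a within-arm mean reduction of 1.3 a low treatment effect. It gives the interval (0.23, 2.37), notes that zero lies outside it, and concludes: "This means if the treatment is effective, we expect to have sufficient sample size to see a result". SAP 10.1 says the study "will evaluate the efficacy of eCoin in reducing episodes of UUI per day with two different treatment arms" and summarises the mean reduction with a 95% interval for each arm and for all subjects. SAP 10.4.1 labels those with at least a 50% fall as responding to treatment.

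**Disclaimers.** The SAP synopsis and 10.1 call the primary endpoint exploratory, with no success criterion and no powered comparison between arms. SAP 5.1 calls the objectives descriptive.

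**The concern.** A subject enters only if the qualifying diary shows an episode on every day. Some qualify because those three days were worse than their usual. Their next diary falls on average without any treatment effect, and because the qualifying diary is the reference, that fall counts as reduction. No arm shows what would have happened without stimulation, so placebo response and natural course are also included.

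Zero is therefore not the no-effect value for an arm's mean reduction. The reasoning in SAP section 6 and protocol 2-6-5 works only if it is. At stake is how the results are read: both arms could show intervals above zero and be taken as two settings that work. The design cannot support that within-arm conclusion. It matters most for subsensory stimulation, whose effectiveness the trial sets out to explore.

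**Working it through.** **1. The plan's own figure.** Inputs from SAP section 6: two-sided alpha 0.05, SD 2, assumed reduction 1.3. D = t(0.975, n−1) × SD / √n.
- n = 16: 2.131 × 2 / 4 = 1.066, so 1.3 ± 1.066 = (0.23, 2.37). This matches.
- n = 13: 2.179 × 2 / 3.606 = 1.209. This matches 1.21. (16 × 0.85 = 13.6, taken as 13.)

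All eight rows of the precision table reproduce to within 0.01. The arithmetic is sound; the issue is the comparison with zero.

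**2. The no-effect value in closed form.** Suppose every subject has the same daily rate λ with Poisson counts (an assumption). Given at least one episode on each baseline day, the expected baseline is λ / (1 − e^−λ), while the expected follow-up is λ. The expected reduction with no effect is the difference:

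| λ per day | 1 | 1.5 | 2 | 3 | 4 |
|---|---|---|---|---|---|
| Reduction | 0.58 | 0.43 | 0.31 | 0.16 | 0.08 |

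**3. Allowing subjects to differ.** The documents give no baseline rate, between-subject spread or day-to-day variance, so these are assumed. True rates are gamma distributed, daily counts are Poisson, subjects are kept only if all three baseline days have an episode, and the treatment effect is zero (400,000 subjects per setting).

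| Population mean / SD per day | 2 / 1.5 | 3 / 2 | 4 / 2.5 | 5 / 3 |
|---|---|---|---|---|
| Mean reduction, no extra diary variation | 0.25 | 0.18 | 0.11 | 0.09 |
| Mean reduction, diary-level CV 0.3 | 0.38 | 0.29 | 0.22 | 0.17 |
| At least 50% fall, no extra variation | 18% | 13% | 9% | 7% |
| At least 50% fall, diary-level CV 0.3 | 26% | 21% | 18% | 16% |

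At n = 16 an arm's 95% interval lies wholly above zero about 4% to 14% of the time, against a nominal 2.5%.

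**4. Wider assumptions.** Mean rate 1.5 to 5, between-subject CV 0.5 or 0.8, daily variance equal to or twice the mean (2,000,000 subjects per scenario). The mean reduction is 0.08 to 0.68: 0.31 to 0.68 at rate 1.5, and 0.08 to 0.22 at rate 5. The interval lies above zero 4% to 38% of the time at n = 16. Without selection, the same model gives a mean reduction of zero apart from simulation error.

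**5. The 50% proportion.** Under the wider assumptions the no-effect proportion is 6% to 37% with selection and 7% to 34% without. In the model of step 3 it is 7% to 26% with and 8% to 26% without. It is mostly diary noise, not selection.

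**6. Adding non-specific response.** Let δ be the total shift from selection, placebo and time; its size is assumed. The chance that the interval excludes zero on the upper side comes from a noncentral t with parameter δ√n / SD. At n = 16:

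| δ per day | 0.5 | 0.75 | 1.0 |
|---|---|---|---|
| SD 2 (plan's value) | 15% | 29% | 47% |
| SD 1.4 (pivotal subset, 8 weeks) | 27% | 52% | 76% |

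**7. Against the pivotal subset.** With mean 2.3, SD 1.4 and n = 16, the lower limit is 2.3 − 2.131 × 1.4 / 4 = 1.55. That is above every selection-only value found here.

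**8. The randomised contrast.** Half-width for the difference in means is t(0.975, 2n−2) × SD × √(2/n). With SD 2, at 16 per arm it is 2.042 × 2 × 0.354 = 1.44; at 13 per arm it is 1.62.

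**The case against.** The strongest reply is that the SAP sets no decision rule. Section 10.1 plans descriptive statistics and an interval, and itself says the endpoint is exploratory with no success criterion. Zero appears only in the sample-size text, which justifies n and does not govern reporting. This stands against a reader who infers that 10.1 tests each arm against zero, or that the plan commits to declaring a setting effective; neither document says so. It does not rescue section 6. The disclaimers cover success rules and between-arm power, and leave uncorrected the step from an interval excluding zero to an effect being seen.

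A second reply is that the selection effect is small and assumption-driven. It largely stands. Only three of the eight reductions in step 3 exceed the plan's illustrative lower limit of 0.23, and that illustration is deliberately cautious. At high episode rates the selection effect is minor.

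A third concerns the 50% proportion. A reader might infer that selection inflates it and that the SAP reads it against zero. SAP 10.4.1 compares it with nothing, and step 5 shows that selection hardly changes it. Only the label is at fault.

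A fourth is that selection precedes randomisation (protocol 2-4-8, SAP 5.3), so it should affect both arms equally. That is correct, and it points to the between-arm difference as the quantity to report. SAP 10.1 allows an optional effect size such as Cohen's d but plans no interval for that difference.

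**Conclusion.** The point holds for the within-arm mean reduction. The qualifying diary is the baseline and neither arm is unstimulated, so the no-effect value is above zero. SAP section 6 and protocol 2-6-5 treat it as zero, and 10.1 attaches efficacy wording to the same per-arm figures.

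From selection alone, the size is about 0.1 to 0.4 episodes per day for assumed mean rates of 2 to 5, and up to about 0.7 under wider assumptions. Placebo or time effects would add to this; the documents give no figure. These are ranges under assumed count models, not estimates for this population.

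Two stronger conclusions do not follow. Selection alone would not produce a reduction of 2.3, so the point does not show that a pivotal-sized change is an artefact. Nor does it bias the sensory-versus-subsensory contrast, since it is expected to be equal in both arms. The matter is one of interpretation in an exploratory trial and can be settled by wording before analysis.

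**What to change.** - **SAP section 6 and protocol 2-6-5:** justify n by the precision of each arm's mean change only. Delete the step from an interval excluding zero to an effect being seen.
- **SAP 10.1:** state that per-arm and pooled reductions are uncontrolled changes from a selected baseline, that they include regression to the mean and non-specific response, and that an interval excluding zero will not be reported as evidence that a setting works.
- **SAP 10.4.1:** call the result the proportion with at least a 50% reduction, a descriptive figure, and drop the label of response to treatment. Diary noise alone gives a non-zero rate.
- **SAP 10.1, addition:** report the randomised between-arm difference with its 95% interval as the interpretable, exploratory contrast. State its expected half-width (about 1.4 at 16 per arm with SD 2) so that nobody expects it to be precise.

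The cost is wording, one extra table row and a weaker within-arm claim. Visits, sample size and treatment are unchanged.

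Optionally, for subjects not yet activated, a 3-day diary before activation would give a reference not used for selection. It would not control for placebo response or natural course, and it needs a protocol amendment with IRB approval (protocol 2-7-7), a CRF change and three more days of recording per subject.

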This study will aim to enroll approximately 40 subjects with a maximum of 50 subjects with a 1:1 randomization. An equal number of subjects will be assigned to each arm of the study. Each subject will participate in the study for up to 7 months (up to 3 months between screening and device activation plus up to 4 months of follow-up).

Key Inclusion Criteria

The target population will be adults above 18 years old with daily UUI with a predominantly urgency component. All subjects must be intolerant of, or show an inadequate response to, at least one second or third-line therapy, i.e., drug or peripheral nerve percutaneous neurostimulation, prior to enrollment. Subjects should be appropriate for eCoin therapy based on the US-FDA approved IFU requirements.

Key Exclusion Criteria

Key exclusion criteria include neurogenic bladder dysfunction, abnormal post-void residual, recent anti-stress incontinence operation, bladder pain

syndrome, peripheral neuropathy, lower leg varicosities, venous insufficiency with skin changes or pitting edema near the ankle, or peripheral arterial disease. OAB medications should be washed out at least two weeks prior to baseline while prior percutaneous tibial nerve stimulation (PTNS) and onabotulinumtoxinA patients should have washout periods of one and nine months respectively.

Primary Endpoints

The primary endpoint is to explore the effect of two different eCoin amplitude settings on the reduction of UUI episodes per day on a 3-day voiding diary after 3 months of eCoin tibial nerve stimulation.

Secondary Endpoints

The secondary endpoints are:

1. Change from baseline in the patient reported quality of life as assessed by the Health Related Quality of Life (HRQL) portion of the Overactive Bladder questionnaire (OABq) survey after 2, 3, and 4 months of therapy.
2. Reduction from baseline in the number of urgency urinary incontinence episodes per day on a 3-day voiding diary (72 hours) after 2 and 4 months of eCoin tibial nerve stimulation.
3. Improvement from baseline of patient satisfaction with UUI symptoms as gathered from patient satisfaction surveys after 2, 3 and 4 months of therapy.

Follow-up

The study flow consists of

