## 6. Sample Size Determination

This study will explore the effect of two programming methodologies (sensory and subsensory amplitude) on reduction of UUI episodes per day as compared to baseline. Change of average UUI per day at 3-months follow-up will be summarized with descriptive statistics for each study arm.

As detailed below, the minimum sample size required for this study is 32 subjects (16 per arm). The planned enrollment of 40 subjects implanted and up to 50 meets this minimum. From the pivotal study, a total of n=133 patients were implanted with eCoin. Looking at the subset of patients programmed at or below sensory level, after 8 weeks of therapy there was a mean reduction in UUI episodes of 2.3 with a standard deviation of 1.4, After 12 weeks of therapy, there was a mean reduction in UUI episodes of 2.7 with a standard deviation of 1.8 per day (n=22). Based on a confidence interval using a t-distribution, a two-sided type-I error rate of 0.05, and using a standard deviation of 2, precision was calculated for a range of sample sizes using the equation below based on the PASS One Mean Module with Tolerance Probability. Margin of error, also known as precision, is the distance between the mean and edge of an interval.

$$D = \frac{t_{1-\alpha/2, n-1} * \hat{\sigma}}{\sqrt{n}}$$

| Sample Size | Precision |
|-------------|-----------|
| 13          | 1.21      |
| 14          | 1.15      |
| 15          | 1.11      |

|    |      |
|----|------|
| 16 | 1.07 |
| 17 | 1.03 |
| 18 | 0.99 |
| 19 | 0.96 |
| 20 | 0.94 |

\*Standard deviation=2

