### 8.2.5. Change from Baseline

Change from baseline will be calculated for the key primary and secondary endpoints for both UUI data and HRQL data.

Change from baseline will be calculated as follows:

$$\text{CFB} = \text{Post-baseline UUI Episodes per day} - \text{UUI Episodes per day at baseline}$$

For HRQL data, change from baseline will be calculated using the composite score as follows:

$$\text{CFB: Post-baseline composite score} - \text{Baseline composite score}$$

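### The arms' raw mean reductions are set side by side with no adjustment for baseline UUI, and no committed baseline table shows whether the analysed arms started alike

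*SAP*

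**What the plan says.** The primary analysis (SAP 10.1) is descriptive and is run in the per-protocol set: "the mean reduction of UUI episodes per day along with its two-sided 95% confidence interval will be summarized" for all subjects, the sensory arm and the subsensory arm. The outcome is a simple difference. SAP 8.2.5 states "Change from baseline will be calculated for the key primary and secondary endpoints for both UUI data and HRQL data", defined as the post-baseline value minus the baseline value with no covariate. SAP 5.3 specifies variable blocks and no stratification. Neither document contains a baseline-adjusted analysis.

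On baseline comparability, SAP 9.7 says "Demographic and baseline characteristics will be summarized by age, gender, ethnicity, race, current smoking status", and adds OAB history and multiple-choice CRF items. Diary UUI/day and the HRQL score are not listed, and the summary is for all implanted subjects. SAP 8 provides columns for all subjects and for each arm. Plots of observed values are optional in 10.1 and 10.2.

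SAP 9.6 lists departures that count against per-protocol status. Two are specific to one arm: no identifiable sensory level (sensory arm), and a threshold at the lowest setting (subsensory arm).

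SAP 6 plans precision for a single arm's mean, with "a two-sided type-I error rate of 0.05, and using a standard deviation of 2", and compares it with "a low assumed treatment effect as a mean reduction of 1.3".

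**The concern.** A subject cannot lose more episodes than they start with. Entry requires at least one urge leak on each of three diary days and sets no upper limit. Because the reduction is baseline minus follow-up, any random excess in the baseline diary also enters the reduction directly. Absolute reduction is therefore likely to rise with baseline frequency.

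The stated aim is to explore the effect of two programming methods, and SAP 10.1 allows Cohen's d to bring out observed differences. Readers will compare the arms. With roughly 13 to 20 subjects per arm, part of any gap may reflect who was in each arm and not how the device was programmed. In the per-protocol set the balance given by randomisation is no longer protected. The one committed baseline table omits the relevant variable and describes a different set of subjects.

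**Working it through.** **1. The plan's own figure.** SAP 6 uses D = t(0.975, n−1) × SD/√n with SD = 2.
- n = 16: D = 1.066 (plan: 1.07); 1.3 ± 1.07 gives (0.23, 2.37), as stated.
- n = 13: D = 1.209 (plan: 1.21).
- All eight rows, n = 13 to 20, reproduce.

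This is the precision of one arm's unadjusted mean. The plan gives no precision for the arm difference.

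**2. Inputs.** SD of change is 2 (SAP 6; the pivotal subset gave 1.8 at 12 weeks). The sizes 13 and 16 per arm are from SAP 6; 20 per arm follows from 40 subjects at 1:1. The correlation r between baseline and reduction is not in the documents, so 0.3, 0.5 and 0.7 are assumed. As a guide, if the baseline and month-3 diaries have equal SD and correlation ρ, then r = √((1−ρ)/2). So ρ = 0.8, 0.5 and 0.3 give r = 0.32, 0.50 and 0.59. On that model r = 0.7 is at the upper end.

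**3. Effect of a baseline imbalance.** The standard error of the baseline difference, in baseline SDs, is √(2/n): 0.392 at n = 13 and 0.354 at n = 16. The shift in the raw arm contrast is r × 2 × imbalance.

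| n per arm | imbalance | r = 0.3 | r = 0.5 | r = 0.7 |
|---|---|---|---|---|
| 13 | 1 SE (0.392 SD) | 0.24 | 0.39 | 0.55 |
| 13 | 1.96 SE (0.769 SD) | 0.46 | 0.77 | 1.08 |
| 16 | 1 SE (0.354 SD) | 0.21 | 0.35 | 0.49 |

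Units are episodes/day, with no true difference between arms. A chance imbalance above 0.5 SD has probability of about 20% at 13 per arm and 16% at 16 per arm. With SD 1.8 every shift is multiplied by 0.9.

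**4. Half-width of the arm difference.**
- Unadjusted: t(0.975, 2n−2) × 2 × √(2/n).
- Adjusted: t(0.975, 2n−3) × 2 × √(1−r²) × √(2/n) × √(1 + 1/(2n−4)).

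| n per arm | unadjusted | r = 0.3 | r = 0.5 | r = 0.7 |
|---|---|---|---|---|
| 13 | 1.62 | 1.58 | 1.44 | 1.19 |
| 16 | 1.44 | 1.40 | 1.27 | 1.05 |
| 20 | 1.28 | 1.24 | 1.13 | 0.93 |

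At 16 per arm the interval is about 3%, 12% and 27% narrower.

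**5. Arm-specific exclusions.** SAP 6 cites pivotal rates of 6.15% with no identified threshold and 3.85% with a threshold of 0.5 mA. At 20 per arm that is 20 × 0.0615 = 1.2 expected exclusions from the sensory arm and 20 × 0.0385 = 0.8 from the subsensory arm. These two routes remove about one subject per arm. Drug use, reprogramming and other deviations add to that at rates that may differ by arm.

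**6. Adjusted arm means.** The adjusted mean of one arm is evaluated at the pooled sample baseline, which is itself random. With two equal arms its true SD is the raw SD × √(1−r²/2), which is 0.87 at r = 0.7. The usual model-based standard error uses √(1−r²), which is 0.71. At 16 per arm the nominal 95% interval then reaches only 2.045 × 0.714/0.869 = 1.68 true SDs, so it covers the population mean about 90% of the time. At r = 0.8 the figure is 2.045 × 0.600/0.825 = 1.49, or about 86%. Simulation gave the same picture: about 90% and 85–86%, with 95% for the adjusted arm difference.

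**The case against.** The plan is openly exploratory. It sets no success criterion and claims no power to compare the arms. For that purpose a raw mean change with a t-interval is valid, and its planned precision reproduces. Some handling of baseline already exists: the 50% responder proportion in SAP 10.4.1 is relative to each subject's own baseline, SAP 10.3 repeats the efficacy analyses in the ITT set, and optional plots could show observed baseline values. The size of any gain rests on a correlation that the documents do not give, and at r = 0.3 the gain in precision is only about 3%.

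Most of this stands, and it makes the point one of interpretation. It does not remove it. A descriptive comparison still needs to show whether the groups began alike. The responder proportion is dichotomised, the ITT set has no baseline diary table either, and the plots are not committed.

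Three stronger readings are tempting and are not supported:
- A reader might infer that adjustment would cut the single-arm half-width by √(1−r²), for example from 1.07 to 0.76 at r = 0.7. That factor belongs to the arm difference. For one arm's mean the gain is to about 0.93 (1.066 × 0.87), and the all-subjects mean gains essentially nothing.
- A reader might infer that adjusted arm means with model-based intervals should replace the raw ones. Step 6 shows that those intervals under-cover.
- A reader might infer that the arm with the higher baseline must show the larger reduction whatever the programming. With no true difference the probability is 0.5 + arcsin(r)/π, or 60%, 67% and 75% at r = 0.3, 0.5 and 0.7. The one-SE shifts in step 3 are also smaller than the standard error of the raw difference (0.78 at n = 13, 0.71 at n = 16).

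**Conclusion.** The point holds as a weakness in how the arm comparison can be read. It is not an error in a test, in the sample size or in the single-arm intervals. No baseline adjustment or stratification is planned, and baseline UUI/day and HRQL are missing from the listed baseline characteristics. The baseline summary also does not describe the per-protocol set that carries the primary result.

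If the SD of change is 2 and r lies between 0.3 and 0.7, an ordinary one-SE imbalance at 13 per arm moves the raw contrast by about 0.24 to 0.55 episodes/day. Adjustment narrows the interval for the arm difference at 16 per arm by about 3% to 27%. Because r is assumed, the precision gain could be negligible, so the firmer case is protection against imbalance and making it visible. The threshold-based exclusions are expected to be few. They are a reason to tabulate the per-protocol set, not evidence of a large bias.

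**What to change.** - **SAP 10.1:** keep the raw arm means with their 95% CIs. Add, labelled descriptive, the between-arm difference in month-3 change in UUI/day from a linear model on arm and baseline UUI/day, with 95% CI, in the PP and ITT sets.
- **SAP 10.2:** do the same for HRQL change at month 3, with baseline HRQL as the covariate.
- **SAP 9.7:** add baseline UUI/day and baseline HRQL by arm for the PP and ITT sets.
- State that model-based CIs of adjusted arm means will not replace the raw CIs.

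The cost is one extra model per endpoint and one extra table, with no new data or visits. Under SAP 8.4 the change should be documented and approved before database lock and unblinding; a change made after lock would have to be labelled exploratory.
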